the participant for this concealment. Allocation sequence will be generated, and the oblique envelopes will be created with the sequence in it and each envelop only open after patient consented and enrolled in the study to determine which treatment the participant will receive.

Blinding

Open label study as True blinding for patients and the research nurse who will apply the topical agent will be difficult as there is a significant difference among the two treatment methods in presentation, colour, density, and odour. the author who will enroll the patients to the study will be blind to treatment assignment. To maintain the blinded status on assessment of outcomes, outcome assessors will be also blinded to treatment allocation.

Study Procedure:

After getting official permission from KAMC IRB, the subject will be randomized using electronic randomization 1:1 ratio. The randomization list was generated electronically through R using the Random Allocation Rule. The data will be collected using Assessment sheet of patient with second stage pressure ulcer tool. Patients will equally be allocated into 2 groups randomly. The zinc oxide group will receive topical zinc oxide twice every 12 hours daily and patients in the MEBO group will receive topical MEBO ointment twice every 12 daily.

The research nurse will be instructed on how to apply the ointment on different surface areas (into and around the edge of ulcers) according to the fingertip unit (FTU). One FTU contains approximately 0.5 g of the ointment. Amounts that were applied to different parts were 7 FTUs for back, 3 FTUs for 1 arm, 1 FTU for both sides of 1 hand, 6 FTUs for 1 leg, and 2 FTUs for 1 foot. The number

Impact of using zinc oxide versus Moist Exposed Wound Ointment (MEBO) in treatment of second stage pressure ulcer: A randomized control clinical trial.

of FTUs applied will be altered by the size of the ulcer. For example, if the patient has a large ulcer on the heel, more ointment was applied in comparison to a small ulcer on a patient's back. For infection prevention, povidone iodine will be used to clean pressure ulcers before MEBO or zinc oxide intervention. Then, the pressure ulcers will be cleansed with normal saline gauze. MEBO will be smeared successively onto the wounds at a thickness of 1mm twice daily with a sterile gloved finger. The same application will be used as for zinc oxide ointment.

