The sample size for the study calculated using the following formula based on the study of Li et al (2017).

$$\text{Sample size (n)} = \frac{p_1(1-p_1) + p_2(1-p_2)}{(p_1-p_2)^2} * C$$

n = Sample size for one group that we need to find out

p1 and p2 = Proportion of two groups

C = Standard value for the corresponding level of α and β selected for the study $(0.84+1.96)^2$.

- 9 -

Short Title: Impact of using Zinc Oxide versus Moist Exposed Wound Ointment (MEBO) in treatment of second stage pressure ulcer: A randomized control clinical trial.

Version: 5.0 (Dated 28-Mar-2023)

Effective date: 29-Mar-2023

Expiration date: 29-Mar-2024

Impact of using zinc oxide versus Moist Exposed Wound Ointment (MEBO) in treatment of second stage pressure ulcer: A randomized control clinical trial.

$n= 0.5 (1-0.5) + 0.167 (1-0.167) (0.84+1.96)^2 / (0.5-0.167)^2 = 27.5 \approx 28$ patients, in addition to attrition rate 20 % therefore sample size will be 34 patients for each group.

A total number 76 patients will be included in the study. A number of eight participants will be included in the pilot study which will equal 10% of the total study number and will be excluded from the study.

Duration of the Study: 12 months in total. The enrolment will be for six months. Follow up will be for maximum 1 months for each subject. A period of 6 months will be for analysis and closing.

Setting:

This study will be carried out at medical ward, neuroscience ward, and intensive care unit at King Abdullah Medical City, Holy Makkah.

Data Collection and Management:

After the official approval from KAMC IRB and the local authority approval. The principal investigator will have a meeting with the team for study implementation overview to ensure the quality and compliance. Researcher will explain the study to the participants and take written consent if they want to participate. For unconscious patient written approval will be taken from there Legally Acceptable Representative. The participation will be voluntary and anonymously. In case of passing away the collected data will not be used and safety reports will be submitted as per the local gaudiness. In case of discharge the collected data will not be used and the patient will be excluded. All data collection sheets will be kept in a locked file cabinet with the researchers.

- 10 -

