Short Title: Impact of using Zinc Oxide versus Moist Exposed Wound Ointment (MEBO) in treatment of second stage pressure ulcer: A randomized control clinical trial.

Version: 5.0 (Dated 28-Mar-2023)

Effective date: 29-Mar-2023

Expiration date: 29-Mar-2024

Impact of using zinc oxide versus Moist Exposed Wound Ointment (MEBO) in treatment of second stage pressure ulcer: A randomized control clinical trial.

Study outcome measurement:

Data will be collected through one tool that will be collected by the assessor daily. It will include two sections as follows:

Section I: Patients' demographic data

This section was developed by the PI based on relevant literature. It will include demographic and medical history data will be collected from the patients' medical records without identifier such as age, sex, body mass index, history of smoking, diagnosis at the time of admission, and laboratory parameters including erythrocyte sedimentation rate (ESR) and C-reactive protein (CRP) will be recorded. Nutritional status of patients will be evaluated considering route of nutritional support (enteral or parenteral). Subject will be identify via serial codes.

Section II: Pressure ulcer assessment.

This section will be adopted from Bates-Jensen 2010 [31]. The Bates-Jensen Wound Assessment Tool (BWAT) will be used to evaluate wound healing. It is a validated wound assessment tool which is used in many healthcare settings for wound assessment. BWAT is straight forward to use and allows nurses to have an objective, comprehensive assessment of wounds. It consists of 13 items to evaluate wound size, type and depth, amount of necrotic tissue, amount and characteristics of exudate, the presence of granulation tissue, epithelialization, and peri- 6 wound skin. PU length and width was measured with a disposable ruler and expressed as cm². Patient will be examined daily till complete healing for the pressure ulcer and maximum one month. If the pressure ulcer not healed within the month of the treatment duration this patient will return to routine care of the hospital. If the any patient will be unable to continue the study because of death, discharge, or change in the care setting the researcher will be excluded from the study.

Each item is graded on a scale of 1 to 5, where a score of 1 indicates progress toward healing while a score of 5 indicates the absence of healing or wound deterioration. Cumulative BWAT scores vary

- 11 -

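### 34 patients per group do not cover the stated 20% attrition: 27.2 remain where 28 are required, and 28 / 0.8 gives 35

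*Protocol*

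**What the plan says.** The section on sample size calculation uses a two-proportion formula with proportions 0.5 and 0.167 and the constant (0.84 + 1.96)², which corresponds to a two-sided 5% level and 80% power. The protocol defines its result as "n = Sample size for one group that we need to find out" and reports 27.5, rounded to 28. The attrition step follows in one clause: "in addition to attrition rate 20 % therefore sample size will be 34 patients for each group". The total of 76 is twice 34 plus the eight pilot patients.

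Two other places settle what happens to a lost patient. Data Collection and Management states, "In case of passing away the collected data will not be used", and also, "In case of discharge the collected data will not be used and the patient will be excluded". Study Procedure and Study outcome measurement both provide for exclusion of anyone "unable to continue the study because of death, discharge, or change in the care setting". Read literally, those last two sentences exclude the researcher, but they can only mean the patient.

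**The concern.** An attrition rate is a fraction of the patients enrolled. To have 28 left after losing 20%, the 28 must be divided by 0.8. Multiplying by 1.2 adds 20% of the smaller number and falls short. The stated 34 looks like the product of that multiplication.

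If so, the trial misses its own evaluable target at its own attrition rate, and the 80% power implied by the constant 0.84 is slightly overstated. In many trials some data from patients who leave early would still be analysed. This protocol sets such data aside after death or discharge, so each of these losses lowers the analysed number by one.

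**Working it through.** **Inputs** (all from the sample size section unless noted)
- p1 = 0.5 and p2 = 0.167
- C = (0.84 + 1.96)² = 7.84
- Attrition 20%
- Stated size 34 per group, allocated 1:1 (allocation from Study Procedure)

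**Step 1: reproduce the base size.** The general formula is n = [p1(1 − p1) + p2(1 − p2)] x C / (p1 − p2)². The protocol's numeric line omits the brackets around the sum; I read it with them, as in the general formula.
- Sum of variances: 0.25 + 0.167 x 0.833 = 0.389111
- Squared difference: 0.333² = 0.110889
- n = 0.389111 x 7.84 / 0.110889 = 27.51, rounded up to 28

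This agrees with the protocol.

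**Step 2: reproduce the 34.** 28 x 1.2 = 33.6, rounded up to 34. Since the step is not printed, this route is an inference. The next check does not depend on it.

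**Step 3: apply 20% loss to 34.**
- Expected losses: 34 x 0.2 = 6.8
- Remaining: 34 x 0.8 = 27.2, below both 28 and 27.51
- Losses that still leave 28: 34 − 28 = 6, which is 6 / 34 = 17.6%

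**Step 4: size that meets the target.**
- From the rounded figure: 28 / 0.8 = 35
- From the unrounded figure: 27.51 / 0.8 = 34.39, rounded up to 35
- Check: 35 x 0.8 = 28
- Totals: 70 randomised instead of 68, or 78 instead of 76 with the eight pilot patients

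**Step 5: power by the protocol's own formula.** Solving the formula for power gives Φ(0.333 x √(n / 0.389111) − 1.96).

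| Evaluable per group | Power |
|---|---|
| 27 | 79.2% |
| 27.2 | 79.5% |
| 28 | 80.6% |

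**The case against.** The strongest reply is that the sentence can be read literally as adding 20% to 28. On that reading 34 contains no slip of calculation, and the protocol never says in so many words that 28 must remain after 20% of those enrolled are lost. This explains where 34 comes from. It does not make 34 sufficient, because the 20% is called an attrition rate and 34 covers a loss of only 17.6%. The fault therefore lies in the inflation method.

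A second reply is that one patient per group is finer than the calculation deserves. That is fair. With the same proportions, a pooled-variance formula gives 31 per group and a continuity-corrected one gives 37, and the protocol gives no source for the 20%. The point cannot be rated as more than a minor correction.

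A third reply is that the power figures apply only to a comparison of two proportions, while the protocol measures its primary objective by the daily Bates-Jensen score. This also stands as a limit: 79% against 80% is the power of the stated formula and not necessarily that of the primary analysis. The shortfall in patient numbers is unaffected.

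**Conclusion.** The concern holds and is minor. At the stated attrition rate, 34 per group leaves 27.2 evaluable patients against a requirement of 28, and the figure that meets the requirement is 35. The shortfall is one patient per group, or two in total. Power by the protocol's formula is about 0.5 percentage points below the nominal 80% at 27.2 per group, and 0.8 points below at 27.

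The conclusion takes the 20% as a fraction of those enrolled and assumes that lost patients do not enter the analysis. The second assumption is what the protocol states for deaths and discharges. It accepts the protocol's proportions, formula and attrition rate as given, and does not judge whether they are realistic. Nothing here threatens the validity of the trial.

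**What to change.** Correct the sentence in the sample size section in one of two ways.

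- **Keep 34 per group** and state that 20% attrition leaves about 27 evaluable per group, with about 79% power by the protocol's formula. This needs no extra patients.
- **State 35 per group**, showing the step 28 / 0.8 = 35, and carry it through to 70 randomised and 78 including the pilot. This costs two more randomised patients.

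Either is acceptable. In both cases, print the attrition step so that a reader can follow it.

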A network meta-analysis (2017) about dressings and topical agents for treating pressure ulcers (Review) of data from 39 studies (evaluating 21 dressings and topical agents for pressure ulcers) concluded that consequently we are unable to determine which dressings or topical agents are the most likely to heal pressure ulcers and more research is needed to determine whether particular dressings or topical agents improve the probability of healing of pressure ulcers [29]. Moreover Boyko et al. (2018), in a review of the current management of pressure ulcers, stated that despite many treatments available, none of them is superior to the other, and pressure ulcers remain a debilitating and costly issue. They recommended additional research to develop products more effective in preventing and treating pressure ulcers [20].

The incidence of pressure ulcers will possibly grow rapidly in the future due to increased life expectancy and aging. However, although various methods are used to treat pressure ulcers, no standard therapy has previously been established. After searching the literature there no studies done before to compare the effects of zinc oxide versus MEBO in treatment of second stage pressure ulcer and because there is no standardization for this practice this clinical trial will be conducted to compare the effects of zinc oxide versus MEBO in treatment of second stage pressure ulcer and determine which one is superior to other.

OBJECTIVES:

The **primary objective** of this study is to:

- 4 -

Short Title: Impact of using Zinc Oxide versus Moist Exposed Wound Ointment (MEBO) in treatment of second stage pressure ulcer: A randomized control clinical trial.

Version: 5.0 (Dated 28-Mar-2023)

Effective date: 29-Mar-2023

Expiration date: 29-Mar-2024

Impact of using zinc oxide versus Moist Exposed Wound Ointment (MEBO) in treatment of second stage pressure ulcer: A randomized control clinical trial.

- To evaluate the efficacy of using zinc oxide versus moist exposed wound ointment in treatment of second stage pressure ulcer.

Secondary Objectives

- To determine the recovery time for both ointments.

Objective measures

For the primary objective

Wound healing will be assessed by using Bates–Jensen Wound Assessment Tool (BWAT) daily for both treatments.

For the secondary objective

The duration of treatment will be record at the assessment sheet so Recovery time will be determined from this sheet.

Research Design:

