- Open label randomized control clinical trial study with a pilot study-using questionnaire.

Inclusion Criteria:

- Subjects ≥ 18
- Willing to participate.
- KAMC cases in medical ward, neuroscience ward, and intensive care unit.
- Newly cases diagnosed with second stage pressure ulcer according to the European pressure ulcer advisory panel/national pressure ulcer advisory panel (NPUAP) guidelines.

Exclusion Criteria:

- 5 -

Short Title: Impact of using Zinc Oxide versus Moist Exposed Wound Ointment (MEBO) in treatment of second stage pressure ulcer: A randomized control clinical trial.

Version: 5.0 (Dated 28-Mar-2023)

Effective date: 29-Mar-2023

Expiration date: 29-Mar-2024

Impact of using zinc oxide versus Moist Exposed Wound Ointment (MEBO) in treatment of second stage pressure ulcer: A randomized control clinical trial.

- Subjects under 18
- Not consenting to participate
- Patients with suspected hypersensitivity reactions to any of the topical formulation's ingredients.
- Either a category III or IV pressure ulcer.
- Evidence of deep tissue injury (exudative drainage, purple or maroon localized area of discolored intact skin or blood-filled blister due to pressure damage).
- Signs of wound infection (pus draining from the ulcer, a foul-smelling odour, tenderness, heat and increased redness in the surrounding skin and fever).
- Patients who undertaking other therapies that could affect healing, such as corticosteroids, radiation therapy, or chemotherapy for cancer.
- Heavy smoking (more than 20 cigarettes a day).
- Concomitant chronic disease (e.g., diabetes mellitus or frank vascular disease such as Buerger's disease).
- Patients who unable to continue the study because of death, discharge, or change in the care setting.

Randomization

Simple randomization method will be used through electronic randomization. The randomization list was generated electronically through R using the Random Allocation Rule by research center member who did not directly participate in trial recruitment and enrolment. Research center member will define

- 6 -

Short Title: Impact of using Zinc Oxide versus Moist Exposed Wound Ointment (MEBO) in treatment of second stage pressure ulcer: A randomized control clinical trial.

Version: 5.0 (Dated 28-Mar-2023)

Effective date: 29-Mar-2023

Expiration date: 29-Mar-2024

Impact of using zinc oxide versus Moist Exposed Wound Ointment (MEBO) in treatment of second stage pressure ulcer: A randomized control clinical trial.

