Furthermore, removal of the possible causal factors (pressure, shear, and friction) and control of the related general condition (such as nutrition, cleaning of the wound, and management of comorbid disease and other medical factors such as blood sugar level that might interfere with the healing process) will be considered for all patients as standard of care.

To eliminate the possible complicating factor of treatment interactions, all patients in both groups will receive position change every 2 hours, and mattress that helps to protect the vulnerable skin. If a patient has more than one ulcer, all the ulcers will be treated by the same method of cleansing, applying and changing positions and the same treatment.

Patient will be examined daily till complete healing for the pressure ulcer and maximum one month as it was reported by Li et al. (2017) reported that the use of MEBO for one week did not significantly affect the improvement of pressure ulcer grades [29]. Moreover, a study done by Palese 2015 reported that to achieve complete re-epithelialization in Stage II PUs, it takes approximately 23 days. This is quite a long time if we consider that pressures of only 60 to 70 mm Hg for between 30 and 240 minutes are needed to cause tissue damage. On average, a small ulcer heals 12 days faster compared with those with a surface of 3.1 cm² or greater [30] so patient will follow for maximum one month. If

Impact of using zinc oxide versus Moist Exposed Wound Ointment (MEBO) in treatment of second stage pressure ulcer: A randomized control clinical trial.

the pressure ulcer not healed within the month of the treatment duration this patient will return to routine care of the hospital. If the any patient will be unable to continue the study because of death, discharge, or change in the care setting the researcher will be excluded from the study.

Pilot study:

It will conduct before data collection on 10% of patients to explore feasibility for future RCT, the efficiency, internal validity and fundamentally, the delivery of proposed trial and identify barriers and facilitators. Zinc oxide will be applied to 4 patients twice daily and MEBO will be applied to 4 patients twice daily till complete healing for the pressure ulcer and maximum one month. The study' tool will be tested, and these patients will be excluded from the study, after completion the patient will have routine care for pressure ulcer treatment.

Sample Size calculation:

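### Randomised patients who die, are discharged or move before healing are excluded, and data after death or discharge go unused, so the analysed set depends on the outcome

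*Protocol*

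**What the plan says.** The rule stands in four sections of the protocol:

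- **Exclusion Criteria** lists "Patients who unable to continue the study because of death, discharge, or change in the care setting".
- **Study Procedure** says that a patient "unable to continue the study because of death, discharge, or change in the care setting the researcher will be excluded from the study". The mention of the researcher is evidently a slip; the patient is meant.
- **Study outcome measurement** repeats it: "If the any patient will be unable to continue the study because of death, discharge, or change in the care setting".
- **Data Collection and Management** goes further for two of the three events. For death: "In case of passing away the collected data will not be used". For discharge: "In case of discharge the collected data will not be used and the patient will be excluded". It has no such sentence for a change in care setting.

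Three other statements matter. Under Randomization, the envelope is opened only after consent and enrolment. Follow-up is fixed by "Patient will be examined daily till complete healing for the pressure ulcer and maximum one month". The sample size makes an allowance: "in addition to attrition rate 20 % therefore sample size will be 34 patients for each group". Under Objective measures, the primary objective is assessed by the "Wound Assessment Tool (BWAT) daily for both treatments", and the secondary objective is recovery time, taken from the recorded duration of treatment.

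Nothing in the protocol provides an analysis of all randomised patients that would override these sentences.

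**The concern.** Death, discharge and transfer cannot be known at screening. They happen after allocation, so listing them as exclusion criteria amounts to removing patients from the analysis after randomisation.

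The removal is tied to the outcome. A patient whose ulcers have healed completely has finished the study and can no longer be excluded as unable to continue. One who is still unhealed stays exposed to exclusion for up to a month. Fast healers therefore escape the rule early and slow healers do not. If the arms differ in healing, the excluded fraction differs too, even when patients leave at the same rate in both arms.

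The consequences are:

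- The healed proportion is overstated unless leavers would have healed at least as often as those kept.
- Recorded recovery time is shortened when exit is unrelated to healing.
- The comparison between arms is biased when healing or exit rates differ by arm. With no treatment effect and equal exit rates it is not.
- Deaths produce safety reports but disappear from the efficacy data.
- Once the data are unused, neither the size nor the direction of the bias can be examined.

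The 20% allowance restores numbers; it does not remove the selection. A change in care setting is also left undefined, although three units take part, so it is unclear whether a move between them triggers exclusion.

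**Working it through.** **The plan's own figure.** With p1 = 0.5, p2 = 0.167 and C = (0.84 + 1.96)² = 7.84:

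n = (0.5 × 0.5 + 0.167 × 0.833) / 0.333² × 7.84 = 27.51, rounded to 28. Then 28 × 1.2 = 33.6, rounded to 34 per group. The stated size reproduces. At 20% attrition about 34 × 0.8 = 27 per arm remain.

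**Assumptions.** The protocol does not say which outcome or time p1 and p2 refer to; I take them as healing by day 30. I take all 20% attrition as due to these exits, with a constant daily exit hazard d. Healing follows a Weibull hazard with shape k = 1, 2 or 4. Shape 4 puts the mean healing day in the 50% arm at 23.1, near the 23 days cited under Study Procedure; shape 1 puts it at 13.3.

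**Formulas.** Cumulative healing hazard: −ln(1−p)·(t/30)^k, with density f(t).

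- Healed in study: H = ∫₀³⁰ f(t)·exp(−dt) dt
- Still in and unhealed at day 30: S = (1−p)·exp(−30d)
- Excluded: 1 − H − S
- Proportion reported under the rule: H/(H+S)

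d is solved so that the average exclusion over the two arms is 20%.

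| k | d per day | 50% arm: H, S, excluded | 16.7% arm: H, S, excluded | Reported | Difference |
|---|---|---|---|---|---|
| 1 | 0.00925 | 0.444, 0.379, 0.178 | 0.146, 0.631, 0.222 | 53.9% vs 18.8% | 35.1 |
| 2 | 0.00855 | 0.427, 0.387, 0.186 | 0.141, 0.645, 0.214 | 52.5% vs 18.0% | 34.5 |
| 4 | 0.00807 | 0.416, 0.393, 0.192 | 0.138, 0.654, 0.208 | 51.4% vs 17.4% | 34.0 |

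The true difference is 33.3 points. At 10% loss the rule gives 34.2 to 33.6 (k = 1 to 4), and at 40% loss 37.2 to 34.9. Standard error for k = 1 at 20% loss: √(0.539 × 0.461/28.0 + 0.188 × 0.812/26.4) = 0.121, so about 12 points.

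**Recovery time** (healing day, or 30 if unhealed, among those kept). For k = 1 the means are 20.6 vs 27.0 days instead of 21.6 vs 27.4. For k = 4 they are 26.3 vs 28.9 instead of 26.5 vs 29.0.

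**No treatment effect, unequal exit.** Both arms truly heal at 50%; exclusion of 10% vs 30% is assumed, without support in the document. For k = 1 the rule reports 52.1% vs 57.4%, a false 5.3 points in favour of the arm losing more patients. For k = 4 it is 1.7 points. Type I error is 6.8% and 5.2%. At 15% vs 25% the false difference is 2.7 to 0.9 points; at equal exit it is zero.

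**Exit linked to healing.** Would-be healers leave at r times the rate of the others (k = 1 to 4 in each cell):

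| r | Reported difference (true 33.3) | False difference, 10% vs 30% |
|---|---|---|
| 0.5 | 35.8 to 35.1 | 8.8 to 5.8 |
| 2 | 34.0 to 32.3 | +1.4 to −2.6 |

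At r = 0.5 the type I error in the no-effect case is about 10.1% to 7.1%.

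**Deaths.** If half of the exits are deaths unrelated to healing, the rule still reports 35.1 to 34.0 points. The day-30 cumulative incidence of healing among all randomised, with death competing, is ∫ f(t)·exp(−dt/2) dt. That gives 47.1% vs 15.6% (31.4 points) for k = 1 and 45.6% vs 15.2% (30.4 points) for k = 4.

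**The case against.** The strongest objection is about size. The shape that matches the protocol's own healing time, k = 4, moves the difference by only 0.7 points, the mean duration by about 0.2 days or less, and the type I error to 5.2%. All of this is small beside a standard error of 12 points. Most inputs (hazard shapes, cause of attrition, exit split, share of deaths) are assumptions, and the sign can reverse. This stands: neither the amount nor the direction of bias can be established from the document.

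It is also true that every figure concerns healed proportion or duration. The protocol gives no BWAT mean, standard deviation or analysis time point, so the effect on the primary measure cannot be sized. In the deaths scenario, part of the gap reflects a different target quantity rather than error from the rule.

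On scope, the ban on using data covers death and discharge only; for a change in care setting, exclusion could merely mean leaving follow-up. That nobody removed has fully healed is an inference from the end of follow-up. Read alone, the discharge sentence has no time limit and could even drop patients discharged after healing. The other three sections, which speak of patients unable to continue, support the narrower reading. Some patients with several ulcers may have had one of them heal.

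None of this defends the rule. It is stated in the protocol, so it is not a detail left to an analysis plan, and keeping the data still allows the completers-only analysis.

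**Conclusion.** The concern holds and should be fixed before analysis. The protocol discards randomised patients and their data after events that occur only while healing is incomplete, and nothing in it overrides this. Under exit unrelated to healing and 20% loss, the inflation of the difference is modest (0.7 to 1.8 points on 33.3). A false difference of 1.7 to 5.3 points arises if exits split 10% vs 30% with no effect. Exit linked to healing can raise that to 8.8 points or turn it to −2.6. The seriousness rests on breaking the randomised comparison, removing deaths from the efficacy data and discarding daily BWAT records, and not on a demonstrated large bias.

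**What to change.** Delete death, discharge and change of care setting from the Exclusion Criteria. Delete the matching sentences under Study Procedure and Study outcome measurement, and the two statements under Data Collection and Management that collected data go unused. This concerns which data are kept, not treatment after exit.

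Then state that:

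- all randomised patients are analysed in their assigned arm, with all daily BWAT and healing data up to departure, BWAT remaining the primary measure;
- healing and recovery time are analysed as time to complete healing up to day 30, with discharge or transfer censored, death as a competing event, and the assumption that censoring is unrelated to healing made explicit;
- unhealed at exit counted as not healed, and completers only, are sensitivity analyses;
- numbers and reasons for exit are reported by arm, and a change in care setting is defined.

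The cost is an amendment and slightly more analysis. The named estimators are partly a matter of choice, and none is free of bias. The censoring assumption cannot be tested. If would-be healers leave at half the rate of others, the censored analysis gives 34.3 to 34.6 points (rule: 35.8 to 35.1). At twice the rate it gives 31.7 to 31.4, further from 33.3 than the rule's 34.0 to 32.3. With such linked exit, in the 10% vs 30% no-effect case, it is off by 3.4 to 4.1 points in either direction. Counting exits as not healed gives 29.7 to 27.8 points at 20% loss. In the 10% vs 30% case it gives a false 6.7 to 8.9 points, larger than the rule's own error when exit is unrelated to healing. Hence its place as a sensitivity analysis only.
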